1.0 Background

Stroke and traumatic brain injury (TBI) are leading causes of long-term disability among Veterans and result in the need for care from informal caregivers after discharge to the home setting. There are very few evidence-based, easy-to-deliver follow-up programs after hospitalization to train caregivers in providing care and to support the relationship between the Veteran and his (her) caregiver. The ANSWERS-VA intervention aims to provide the Veteran and caregiver dyad with a set of practical skills that each can use in coping with and managing symptoms of brain injury.

2.0 Rationale and Specific Aims

Project Objectives. The objectives of this study are to conduct a randomized controlled trial (RCT) to evaluate (a) the efficacy of the “Acquiring New Skills While Enhancing Remaining Strengths for Veterans (ANSWERS-VA)” dyadic intervention with Veterans who have sustained a stroke and/or traumatic brain injury (TBI) and their informal caregivers, and (b) estimate effect sizes for the ANSWERS-VA intervention. The ANSWERS-VA intervention will be compared with an educational intervention that will serve as an attention control group.

Specific Aim 1: To tailor the implementation of the ANSWERS-VA intervention to dyads (n=10) consisting of Veterans with stroke and/or TBI diagnoses and their informal caregivers and modify the implementation processes for the RCT.

Specific Aim 2: To test the short-term, intermediate, and sustained efficacy of the intervention (baseline, 8, 12, 24 weeks, and 1 year) for improving the caregivers’ quality of life, task difficulty, threat appraisal, self-efficacy for caregiving, and optimism.

Specific Aim 3: To complete a cost effectiveness analysis of the intervention in comparison to the attention control.

Exploratory Aim 1: To estimate the effect sizes for the dyad outcomes of depressive symptoms, social participation, and quality of the dyadic relationship.

3.0 Inclusion/Exclusion Criteria

For this study, an eligible, informal caregiver is defined as a family member or significant other who is providing care for a Veteran stroke or a TBI survivor in the home setting. Table 2 provides inclusion and exclusion criteria for Veterans and caregivers. Eligibility will be assessed by Veteran and/or caregiver self-report during a screening telephone interview; however, study personnel may do a basic initial screen by accessing electronic medical records in the Computerized Patient Record System (CPRS) when patient lists are obtained.

Table 2. Inclusion and Exclusion Criteria

Inclusion Criteria	Exclusion Criteria

Informal Caregivers Primary caregiver (family member or significant other) of a Veteran stroke or TBI survivor Plans to be providing care for 1 year or longer Task difficulty (OCBS task difficulty score) of 16 or greater
	
Informal Caregivers Caregiver does not consider him or herself a caregiver (i.e., believes that the survivor is not impaired or is the same as before the stroke or TBI) Serious medical illness limiting ability to participate

Veterans Must have had a hemorrhagic or ischemic stroke and/or a TBI Stroke occurred within the last 3 years TBI occurred post-9/11/2001
	
Veterans Resides in a nursing home or long-term care facility Diagnosis of Transient Ischemic Attack (rather than a hemorrhagic or ischemic stroke) Stroke occurred more than 3 years ago TBI prior to 9/11/2001

Both Access to a telephone Willingness to participate in 9 intervention or control calls and 5 data collection interviews at designated study time points Mini-Mental State Examination (MMSE) Score of 4 or above (see Appendix 8.4 in Section 11.0 for MMSE).
	
Both Unable to contact within 10 calls Age < 18 years Either caregiver or Veteran denies that survivor has had a stroke or a TBI Either the caregiver or Veteran does not want to participate Not fluent in the English language Difficulty hearing or talking by telephone Has a terminal illness (e.g., cancer, end of life condition with decreased life expectancy, renal failure requiring dialysis) History of hospitalization for alcohol or drug abuse History of severe mental illness (e.g., Alzheimer's, dementia, suicidal tendencies, severe untreated depression or manic depressive disorder, or schizophrenia) Prisoner or on house arrest

4.0 Procedures

Recruitment-Participant Identification and Screening: The PI, graduate student interns, and the project manager will be involved in participant identification and screening. We will use several methods to identify Veterans with stroke (hemorrhagic or acute ischemic) and TBI and their caregivers:

- 1) To identify Veterans with recent admissions, we will run lists of patients who were admitted and discharged with stroke or TBI diagnoses. A waiver of consent and HIPAA will be obtained and the patients will be screened for inclusion criteria. After obtaining approval from the provider, we will approach the patient and his/her caregiver (in-person, phone, or mail) about participation in the study;
- 2) We will utilize the Veterans Health Information System (Vista) to establish a list of Veterans/caregivers with a diagnosis of stroke within the past 3 years (10/1/2011 thru present) and TBI post-9/11/2001. A waiver of consent and HIPAA will be obtained and the patients will be screened for inclusion criteria. After obtaining approval from the provider, we will approach the patient and his/her caregiver (in-person, phone, or mail) about participation in the study;
- 3) We will seek provider referrals by regularly contacting all services throughout the hospital and Care Managers in Neurology, PM&R/TBI, and the Caregiver Program Case Manager(s); and
- 4) Advertisements will be placed throughout the VA hospital so that Veterans and/or caregivers can contact the study team.

- 5) We will seek research referrals by utilizing lists of patients from other stroke and/or TBI studies for which the PI has been a collaborator (Co-I, Co-PI, or PI). A waiver of consent and HIPAA will be obtained and the patients will be screened for inclusion criteria. After obtaining approval from the provider, we will approach the patient and his/her caregiver (in-person, phone, or mail) about participation in the study;

After the potential participants have been identified through lists or referrals, we will obtain approval from the Veterans' healthcare providers before we make contact regarding the study. Veterans and their caregivers/next of kin will be contacted in several ways: (1) some may be approached while they are in the hospital being treated for stroke or TBI and given a study brochure and basic information to let them know about the study, and (2) others will be mailed a recruitment packet. When a Veteran with a known caregiver is identified, the recruitment packet will contain a recruitment letter, study brochure, 2 copies of the informed consents (VA Informed Consent Form and the VA Consent for Recording) and HIPAA authorization form (one each for the caregiver and the Veteran), and a Volunteering in Research pamphlet (as required by VA) (see Appendix A1.5). When we are unsure whether or not the Veteran has a caregiver, we will mail a recruitment packet that only contains a recruitment letter and our study pamphlet (see Appendix A 1.1). A telephone number will be provided on the recruitment letter for the recipients to call if they do not wish to be contacted for the study. All recruitment materials can be found in Appendices 1.1-1.5 in section 11.0.

Approximately 1 week after recruitment packets are mailed, Veterans and/or their next of kin will be telephoned by study personnel to determine their interest in the study and to screen for eligibility. We will make approximately 10 attempts to phone each potential participant. If initial contact is made while in the hospital, patient and caregiver will be given the opportunity to be screened for eligibility and/or consented prior to discharge. Otherwise, patient and caregiver will be contacted via phone within 1 week of going home.

We will request a waiver of written informed consent and HIPAA authorization for the purposes of screening the potential participants through medical record review and/or discussions with providers, and potential participants will not be contacted by the study team until those waivers are approved by the IRB. We will obtain approval from the Chief of Medical Services, Neurology, Physical Medicine Rehabilitation (PMR), and the ACOS of Primary Care at both study sites to before we conduct the research. After hospital service approvals, Institutional Review Board (IRB), and VA Research & Development (R&D) approvals are received, we will begin recruitment.

Consent and Enrollment. The informed consents and HIPAA authorization will be explained to interested Veterans and their caregivers over the telephone or in-person. If eligible and they consent, the Veterans and their caregivers will sign and return the consents and HIPAA authorization to the study team by mail, fax, or in-person. Each Veteran and caregiver (i.e., dyad) will receive a copy of the signed consents and HIPAA authorization. Consented dyads will then be scheduled for a baseline data collection telephone interview. Data collection will not occur until the consents and HIPAA authorizations are received by the study team.

Randomization to Groups. Following enrollment, the statistician will randomly assign the dyads to either the ANSWERS-VA intervention or the educational attention control group using a block randomized approach with stratification on diagnosis (stroke dyad/TBI dyad), recruitment site (two for stroke dyads, two for TBI dyads), type of relationship (spouse vs. adult child/other),

PTSD (stroke survivor/TBI survivor), and baseline depressive symptoms (non-depressed vs. depressed PHQ-9 > 5). SAS PROC PLAN⁷⁸ will be used to create the randomized blocks within strata in order to obtain, as closely as possible, similar numbers and composition (balance) between the groups, and facilitate maintenance of blinding of data collectors.

Baseline Data Collection. Veterans and their caregivers will be interviewed by a data collector or the project manager for his (her) baseline interview. This interview will be completed by telephone. Interviews are expected to take approximately 30 minutes for the Veterans, and 60 minutes for the caregivers. Veterans and caregivers will be interviewed separately, either back-to-back or scheduled within a week of one another, whichever is most convenient to the dyad. All data collection instruments including a table which reflects when each instrument is used can be found in Appendices 8.1-8.3 (see section 11.0).

ANSWERS-VA Intervention Procedures. The ANSWERS-VA intervention is delivered completely by telephone. Dyads will receive 8 weekly calls (plus a booster call at 12 weeks) from an ANSWERS intervention specialist located in Indianapolis. The first scheduled intervention call is planned to occur within approximately 1 week of baseline.

The intervention specialist will provide each dyad with educational information on topics such as stroke or TBI as well as cognitive abilities, communication, emotions, behaviors, roles, and social activities all of which may be impacted by the stroke or TBI. Then the intervention specialist will work with each dyad to learn skills and techniques that will help the Veteran and caregiver cope with the symptoms and impairments that resulted from the brain injury. The intervention specialist will also help the dyad apply these lessons to tasks or activities that the dyad selects as being important. Thus, the intervention allows for some flexibility to be able to tailor the sessions to the needs of the dyad. Each session will last approximately 60-90 minutes. Dyads assigned to the intervention group will receive:

- 1) the schedule of upcoming study calls (see Appendix 2.2 in section 11.0),
- 2) ANSWERS-VA workbook (see Appendix 12 in section 11.0),
- 3) Veteran Stroke & TBI Resource Guide (see Appendix 5 in section 11.0),
- 4) Be Involved Brochure (see Appendix 13 in section 11.0),
- 5) if the participants are in the TBI arm, and if they have children, a booklet entitled, "Talking with Children about TBI" or "Talking with Children about Moderate or Severe TBI" (whichever is more applicable to the dyad) (see Appendices 4.2 and 4.3 in section 11.0), and
- 6) if the Veteran has a Post-Traumatic Stress Disorder (PTSD) diagnosis, the Veteran PTSD Booklet (see Appendix 6 in section 11.0).

Attention Control Procedures. The attention control procedures are also delivered completely by telephone. Dyads will receive 8 weekly calls (plus a booster call at 12 weeks) from an ANSWERS intervention specialist who has been cross-trained in the attention control procedures located in Indianapolis. The first scheduled attention control call is planned to occur within approximately 1 week of baseline.

The attention control calls will begin by establishing rapport by asking dyads how they are doing. The intervention specialist will then provide support through the use active listening strategies. These strategies include using (a) conversation starters (e.g., "What would you like to talk about today?"), (b) paraphrasing (e.g., "What you are telling me is..."), (c) clarifying (e.g., "Tell me

more about that”), (d) reflection (e.g., “So, you’re feeling ___ because ___”), and (e) summarizing (e.g., “So, overall...”). These strategies provide the dyad with the opportunity to express their problems and concerns and to use the interventionist as a “sounding board.” Intervention specialists will refer dyads to the ASA or TBI organization, or their health care providers for more information and answers to their questions. These calls are expected to last approximately 15-30 minutes. Dyads assigned to the attention control group will receive:

- 1) the schedule of upcoming study calls (see Appendix 2 in section 11.0 for a complete packet of study letters), and
- 2) educational materials entitled, “Caring for Stroke Survivors” published by the American Stroke Association (ASA) (see Appendix 3 in section 11.0) or “Becoming a Family Caregiver for a Service Member/Veteran with TBI” published by the Defense and Veterans Brain Injury Center (DVBIC) (see Appendix 4.1 in section 11.0).

At the end of the dyad’s participation in the study, the attention control group will receive the ANSWERS-VA workbook, Veteran Stroke & TBI Resource Guide, Be Involved Brochure, and the Talking with Children about TBI and Veteran PTSD Booklet if applicable.

Study Withdrawal/Discontinuation. Any subject is permitted to withdraw from the study at any time or decline to answer any particular question without adverse effects. If a subject withdraws, we will complete a standardized form detailing the reason. If one member of the dyad decides to withdraw, then the other member will have to be withdrawn by the study team because the study intervention relies upon the participation of both the Veteran and caregiver.

Treatment Fidelity Procedures for the ANSWERS-VA Intervention and Attention Control

Procedures. Special efforts will be made to boost and track treatment fidelity of both the ANSWERS-VA intervention and attention control procedures. In order to track and monitor treatment fidelity, the intervention and control calls will be audio-recorded with the permission of the Veteran and caregiver.

Data Collection Procedures. Data collectors and the project manager (baseline data collection only) will be trained to conduct telephone surveys for data collection prior to recruitment. Study personnel will work with the dyad to create a schedule of calls for the study. Response forms (see Appendix 7.1-7.3 in section 11.0) will be mailed to the dyads prior to the data collection calls to facilitate the interview process. Data collectors will be blinded to group assignment and will complete the remainder of the data collection calls which will be scheduled for 8 weeks, 12 weeks, 24 weeks and at 1 year following the baseline interview. These interviews are estimated to take 30 minutes with caregivers and 15 minutes with Veterans. Veterans and caregivers will be interviewed separately, either back-to-back or scheduled within a week of one another, whichever is most convenient to the dyad. Surveys/instruments used for data collection can be found in Appendix 8.1-8.3 (see section 11.0). Data will be collected on paper forms, and then entered into an electronic database.

In order to alleviate some of the interview time and burden on the dyad, and to collect accurate data, Veteran demographics and medical history data (i.e., comorbidities, injury-specific data, health care utilization) will be collected via retrospective medical chart review using the VA electronic medical record known as CPRS. A complete list of variables collected can be found on the Veteran chart abstraction form in Appendix 9 in section 11.0. Please note that the only variables which will contain PHI/PII being collected for the Veterans and caregivers during the course of this study are as follows: name, address, telephone number, MRN (Veteran only-MRN

is SSN at VA), date of discharge (Veteran only), date of diagnosis (Veteran only) and the audio recording of the intervention and control sessions. Methods for ensuring privacy and confidentiality for the Veterans and caregivers are discussed in more detail in section 9.0.

[figure not shown]
Payment for Participation. Veterans and caregivers will be reimbursed after completing the baseline and 1-year interviews. Reimbursement will be through gift cards unless the VA specifies another payment method must be used. The schedule and amounts for reimbursement for each participant will be as follows: baseline interview - \$15; 1-year interviews - \$15. The total potential reimbursement for each participant in the study is \$30. The VA protocol for research participant reimbursement will be followed.

Project Management Plan. Overall, the coordination of this project will be led by the VA Indianapolis study team with [name], MSN, RN, the PI, overseeing the project. [name] will coordinate the study investigators, and the project manager and will coordinate the research staff and ensure that this study is compliant with all IRB and VA policies and regulations. Study teams from Indianapolis and Houston will have weekly conference calls. Prior to the initiation of this study, Drs. [name] and [name] will provide training to the intervention specialists for both the ANSWERS-VA intervention and the attention control groups. In addition, all data collectors will undergo training on how to complete the surveys, collect data, and perform data entry to ensure that data from the two sites is being collected in a consistent manner. Yearly face-to-face meetings and weekly calls will ensure that all sites follow the study protocol. The project manager will coordinate prompt and reliable feedback to each site related to any data problems that may occur and likewise, will provide regular recruitment updates. Intervention fidelity will be observed through the review of audio recordings to ensure standardized delivery of the intervention. Data management will be coordinated through the IUSM Biostatistics Department which has coordinated other VA and non-VA multi-site studies.

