Data Analysis. Outcomes will be assessed by trained data collectors who are blinded to the treatment. Caregiver task difficulty, optimism, self-efficacy for caregiving and threat appraisal are proposed as mediators for the intervention effect on the primary outcomes of caregiver's quality of life and unhealthy days. We will test the immediate efficacy of the ANSWERS-VA intervention on these mediators and outcomes from baseline to 8 weeks, and long-term, sustained efficacy at (12 and 24 weeks and at 1 year). Veteran and caregiver characteristics (i.e., demographics, co-morbidities, relationship of caregiver to Veteran, and caregiver assessment of the Veteran's impairment) will be controlled by the stratified randomization process and, as necessary, by covariates included in the models. We will assess the exploratory outcomes of effect sizes for the ANSWERS-VA intervention for the Veteran and caregiver on the secondary outcomes of depressive symptoms, social participation, and quality of the dyadic relationship. We will also assess the outcomes of noncaregiving hours and unhealthy days in caregivers to determine the cost effectiveness of this intervention (see Figure 2).

Figure 2. Research Design v5-19-2014

I denotes weekly intervention nurse calls; IB booster at 12 weeks; A denotes weekly attention control nurse calls; AB attention control booster at 12 weeks. *Data collection calls by blinded research assistants.

Study Timeline. The study timeline is planned for four and a half years. We will devote our efforts to start-up, training, and IRB approvals during year 1 and then proceed to recruitment during months 10-36. We complete the 1-year data collection and data analyses on the primary aims in year 4. In the first quarter of year 5, we will complete the follow-up 1-year data analyses to guide our pre-implementation phase of the ANSWERS-VA intervention (see Gantt Chart in Table 6 below).

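### When one dyad member withdraws, the other must be withdrawn too, and nothing provides for continuing a willing caregiver's primary-outcome interviews, even after the week-12 booster

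*Combined protocol and SAP*

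**What the plan says.** The withdrawal paragraph in Section 4.0 opens with "Any subject is permitted to withdraw from the study at any time". It then states "If a subject withdraws, we will complete a standardized form detailing the reason", and goes on: "If one member of the dyad decides to withdraw, then the other member will have to be withdrawn by the study team". The reason follows directly: "because the study intervention relies upon the participation of both the Veteran and caregiver". The paragraph sets no time limit and does not distinguish leaving the calls from leaving the outcome interviews.

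Other parts of the combined protocol and SAP bear on this:

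- **Outcomes.** Section 5.0 (Data Analysis) names the caregiver's "quality of life and unhealthy days" as the primary outcomes.
- **Interviews.** Section 4.0 (Data Collection Procedures) schedules follow-up at "8 weeks, 12 weeks, 24 weeks and at 1 year following the baseline interview", and "Veterans and caregivers will be interviewed separately".
- **Sessions.** In both arms the last session is the booster call at 12 weeks (Sections 4.0 and 5.0).
- **Missing data.** Section 6.0 undertakes to minimize missing data but lists only operational steps: tracking, scheduling, missing-value codes, backup, paper forms and quarterly inspection.

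**The concern.** The stated reason concerns delivery of the intervention, but the rule reaches further. A Veteran who withdraws at month 5 takes a willing caregiver out of the 24-week and 1-year assessments, although every session has already been given. Those are two of the three time points that Section 5.0 uses for sustained efficacy.

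The certain cost is precision, because primary-outcome data that could have been obtained are not collected and cannot be recovered at analysis. Bias is a further possibility. It needs the arms to differ in how many caregivers are removed this way, or in how those caregivers' outcomes compare with the rest. Unequal withdrawal is plausible, since sessions last 60-90 minutes in the intervention arm and 15-30 minutes in the control arm, but the documents do not show that it will happen.

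**Working it through.** **Text.** The paragraph begins with withdrawal from the study, and the rule follows two sentences later with no narrower scope. Section 5.0 gives no follow-up or analysis rule for withdrawn dyads, Section 6.0 does not mention follow-up after withdrawal, and Section 9.0 only repeats the right to withdraw. Appendix 2 lists a letter (A2.13) for withdrawal during calls IC1-IC8, but its text and the consent forms are not shown.

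**Inputs.** From the documents: 330 dyads (222 stroke + 108 TBI = 330, which agrees). Assumed, because the documents shown give no withdrawal rate, SD or power figure: each member withdraws by 1 year with probability q, and the two withdrawals have correlation φ. Positive correlation is likely, so φ = 0 is the high end.

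**Precision.** With the rule, the proportion of caregivers lost is L = 2q − [q² + φq(1−q)]; without it, q. Extra loss = 330(L − q). Standard-error ratio = √[(1−q)/(1−L)].

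| q | φ = 0 | φ = 0.3 | φ = 0.5 |
|---|---|---|---|
| 5% | 16 lost, SE +2.6% | 11, +1.8% | 8, +1.3% |
| 10% | 30, +5.4% | 21, +3.7% | 15, +2.6% |
| 15% | 42, +8.5% | 29, +5.7% | 21, +4.0% |

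For q = 10%, φ = 0: L = 0.20 − 0.01 = 0.19; 330 × 0.09 = 29.7; √(0.90/0.81) = 1.054. If a design had 80% power at 10% loss (1:1 allocation, two-sided 5%), power at 19% loss would be about 76%.

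**Timing (q = 10%).** At an even withdrawal rate, q by week 8 is 1 − 0.9^(8/52) = 0.0161, so the rule costs about 5 caregivers by then (3 at φ = 0.5). If half of withdrawals fall in the first 12 weeks, q by week 8 is 0.0333 and the cost is about 11 (5). If 25%, 50% or 77% of Veteran-only withdrawals come after week 12 (77% = 40/52, an even rate), then 7, 15 or 23 of the 30 removals come when the stated reason no longer applies (4, 7 or 11 of the 15 at φ = 0.5).

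**Bias (complete-case analysis assumed).** Without the rule, the observed group is the retained caregivers plus those the rule would have removed. The rule therefore shifts an arm's mean by gap × (L − q)/(1 − q), where gap is the outcome difference between lost and retained caregivers. Take L = 20% in one arm and 10% in the other:

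- φ = 0: q = 0.1056 and 0.0513; between-arm difference 0.1056 − 0.0513 = 0.0543.
- φ = 0.5: q = 0.1399 and 0.0682; difference 0.0699 − 0.0341 = 0.0358.

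For a gap of 0.3 to 0.8 SD, the bias is 0.016-0.043 SD (φ = 0) or 0.011-0.029 SD (φ = 0.5). It halves if caregivers removed only because of the Veteran differ half as much. With 15% versus 10% loss and the full gap it is 0.008-0.021 SD (φ = 0) or 0.005-0.014 SD (φ = 0.5). With equal removals and equal gaps it is zero.

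For scale, 330 dyads with no loss detect (1.960 + 0.842) × √(4/330) = 0.308 SD at 80% power. The 20% versus 10% range is about 5-14% of that (3-9% at φ = 0.5).

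**The case against.** **The paragraph never says that interviews stop.** Its reason is about the intervention, so it could mean leaving the intervention only. Appendix 2 also has separate letters for failing to reach participants for intervention calls (A2.11) and for data collection calls (A2.12), so the paperwork treats the two as distinct. This stands as a limit on certainty. Those letters concern failed contact, however, and do not show that interviews continue after a withdrawal. If the narrower reading was meant, the plan still needs to say so.

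**Dyad-level handling has real grounds.** Dyads are randomized, either member's unwillingness excludes the pair, Exploratory Aim 1 concerns dyad outcomes, and some caregiver items are about the Veteran. These justify dyad entry and care over Veteran-related items. None requires dropping the caregiver's own quality of life or unhealthy days.

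**The sizes are assumed and modest.** This is correct. The counts also suppose that every removed caregiver could be reached and would agree, so they are upper-end figures. The top of the bias range needs independence together with a full outcome gap, which is hard to justify. With 15% versus 10% loss, φ = 0.5 and half the gap, the bias is only 0.003-0.007 SD.

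**A retained control caregiver might receive the workbook early.** Section 4.0 gives it at the end of the dyad's participation, which could be taken as the day the Veteran withdraws. Section 7.0 already holds it until the final data collection interview, so the risk is met if that wording governs.

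**Conclusion.** The concern holds and should be fixed. It is certain that the rule is mandatory and that no text shown provides for continued interviews. That interviews therefore stop is the natural reading, held with moderate to high confidence because the consent forms and letters are not available.

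The case rests on needless loss of obtainable primary-outcome data: about 8 to 42 caregivers of 330 by 1 year, and a standard error 1.3% to 8.5% larger, for assumed withdrawal of 5-15% per member and correlation of 0 to 0.5. Relatively little of this falls at 8 weeks; the loss is mainly at 24 weeks and 1 year. Bias is not shown. Its size and direction cannot be settled without withdrawal rates by arm.

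**What to change.** Separate stopping the sessions from leaving data collection, in both the protocol and the consent form.

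1. When one member withdraws, joint sessions end as already written, and nothing changes for the member who withdrew.
2. The other member, if willing, is offered the remaining interviews at 8, 12 and 24 weeks and 1 year, and is analysed in the assigned arm. At minimum, keep the caregiver's own quality of life and unhealthy days.
3. On the existing withdrawal form, record as separate dated events: stopped sessions; withdrew from data collection; removed because the partner withdrew.
4. State which caregiver-reported items about a withdrawn Veteran are omitted.
5. State that a retained control caregiver receives the workbook only after that caregiver's own last interview, in line with Section 7.0.
6. If the rule was only ever meant to end the intervention, say so explicitly.

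**Cost.** A protocol and consent amendment, including the consent position of dyads already enrolled. Item 4 needs thought, because task difficulty, self-efficacy, impairment and relationship items may involve the Veteran and the instruments are not shown. Each retained caregiver adds at most four 30-minute interviews and one 15-dollar payment. For 8 to 42 caregivers the ceiling is 32-168 interviews (16-84 hours) and 120-630 dollars. Allowing for when withdrawals occur, it is about 15-134 interviews (7-67 hours).
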